7.3.1. Study Drug Discontinuation Criteria for Persistent Abnormal Clinical Laboratory Values

If at any time during the study a participant develops elevations in ALT or AST > 3 X ULN, or CK > 5 X ULN, the study site will receive an alert from the central laboratory.

Study drug should be discontinued immediately and permanently when any of the following criteria are met*:

- ALT or AST > 8 X ULN
- ALT or AST > 3 X ULN with bilirubin > 2 X ULN
- ALT or AST > 3 X ULN with the appearance of fatigue, nausea, vomiting, right upper quadrant pain or tenderness, fever, rash, and/or eosinophilia (> 5%)
- Rhabdomyolysis regardless of CK value

Study drug should be discontinued temporarily and requires repeating laboratory testing when any of the following criteria are met*:

- ALT or AST > 3 X ULN
- CK > 10 X ULN

Participants should undergo repeat laboratory measurements as soon as possible, within 72 hours (unless otherwise specified). Repeat laboratory measurements will include those tests outlined in Section 12.1.2.2.1 and Section 12.1.2.2.2. Local laboratory measurements may be used to facilitate follow-up.

If the repeat ALT or AST is > 3 X ULN with International Normalized Ratio (INR) > 1.5, study drug should be discontinued permanently. If the INR is < 1.5 but the ALT or AST is > 5 X ULN and persists beyond 2 weeks, study drug should be discontinued permanently. If the ALT or AST values recover without meeting the discontinuation criteria, study drug can be resumed at the investigator's discretion.

For CK > 10 X ULN, if the repeat CK elevation remains > 5 X ULN and is not explained by exercise or trauma, study drug should be discontinued permanently. If the CK elevation remains > 5 X ULN and is explained by exercise or trauma, the patient may continue therapy and be followed until they have returned to baseline, or the investigator considers them clinically stable. If exercise- or trauma-related elevation does not resolve, the study drug should be discontinued permanently. If the CK values recover without meeting the discontinuation criteria, study drug can be resumed at the investigator's discretion.

^{*}Participants who discontinue study drug are not required to withdraw from the study and should continue all in-person visits and telephone contacts to monitor for AEs and the occurrence of potential endpoint events until the CSED Visit.

Study drug can be continued, but requires repeating laboratory testing when the following criterion is met:

• CK > 5 X ULN but < 10 X ULN

Participants should undergo repeat laboratory measurements as soon as possible, within 72 hours (unless otherwise specified). Repeat laboratory measurements will include those tests outlined in Section 12.1.2.2.2. Local laboratory measurements may be used to facilitate follow-up.

If the CK elevation remains > 5 X ULN and is not explained by exercise or trauma, study drug should be discontinued permanently. If the CK elevation remains > 5 X ULN and is explained by exercise or trauma, the patient may continue therapy and be followed at least weekly until CK values fall below 5 X ULN, at which time the study drug may be resumed by the investigator. If exercise- or trauma-related elevation does not resolve, the study drug should be discontinued permanently.

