7.3. Study Drug Discontinuation

Participants who discontinue study drug are not required to withdraw from the study and should continue all in-person visits and telephone contacts to monitor for AEs and the occurrence of potential endpoint events until the CSED Visit. At a minimum, vital signs should be obtained at in-person visits, but blood draws are at the investigator's discretion until the participant resumes study drug.

It will be necessary to make a distinction between participants who prematurely discontinue study drug treatment and those who withdraw from the study. All study drug discontinuations should be considered temporary interruptions because participants are allowed to restart medication at any time if the condition leading to study drug interruption has resolved, eg, a woman who becomes pregnant while in the study can resume study drug when she is no longer pregnant or breastfeeding. If a participant has discontinued study drug and the investigator has determined that it is appropriate to re-start study drug, then at the investigator's discretion and with prior approval of either the Sponsor or medical monitor, the investigator may elect to re-start the participant on a once a day dose of study drug with the goal of achieving twice daily dosing.

If the participant discontinues study drug, the reason should be captured and could include the following:

- 1. The participant meets any of the criteria specified in Section 7.3.1
- 2. The participant begins to take any medication(s) that is contraindicated by the protocol
- 3. The participant develops an AE that, in the opinion of the investigator, would compromise the participant's safety to continue the study drug
- 4. The participant becomes pregnant
- 5. The participant withdraws consent
- 6. The participant requests discontinuation of the study drug for any reason, or
- 7. In the investigator's judgment, it is in the participant's best interest

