12.1.2.2.1. Liver Function Test Elevations

Refer to Section 7.3.1 for details on study drug discontinuation procedures related to elevated liver function results.

Repeat evaluation should include AST, ALT, prothrombin time/INR, total bilirubin, ALP, GGT, creatinine, CK, and complete viral hepatitis screen. The participant should be questioned regarding symptoms, as well as potential causative factors. This information, including results and normal ranges of any laboratory parameters collected at a local laboratory, should be collected on the appropriate eCRF. Hepatobiliary ultrasonography and/or consultation with a hepatologist should be considered if clinically indicated.

Abnormal laboratory parameters should be followed at least weekly (more frequently as clinically indicated) until they have returned to baseline or have stabilized.

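### The repeat and follow-up tests after a liver-enzyme alert omit a white-cell differential, so eosinophilia (a permanent-stop criterion) can go unmeasured before drug is resumed

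*Protocol*

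**What the plan says.** Protocol Section 7.3.1 has two tiers for raised transaminases. ALT or AST above 3 X ULN alone is a temporary stop with repeat testing within 72 hours. The same level with any one accompanying feature is an immediate, permanent stop. The features include several symptoms and signs and end with "right upper quadrant pain or tenderness, fever, rash, and/or eosinophilia (> 5" (a percentage). Because the list is joined by and/or, eosinophilia alone is enough.

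On the repeat, Section 7.3.1 says: "Repeat laboratory measurements will include those tests outlined in Section 12.1.2.2.1 and Section 12.1.2.2.2". Section 12.1.2.2.1 gives the liver list: "Repeat evaluation should include AST, ALT, prothrombin time/INR, total bilirubin, ALP, GGT, creatinine, CK, and complete viral hepatitis screen". It adds: "The participant should be questioned regarding symptoms, as well as potential causative factors". Abnormal values are then followed at least weekly. The creatine kinase list in Section 12.1.2.2.2 consists of muscle and cardiac markers, creatinine, transaminases, bilirubin and urinalysis. Neither list contains a blood count.

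On restarting, Section 7.3.1 says: "If the ALT or AST values recover without meeting the discontinuation criteria, study drug can be resumed at the investigator's discretion". For participants who are off drug, Section 7.3 says that "blood draws are at the investigator's discretion until the participant resumes study drug".

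Scheduled testing is fuller. Section 12.1.2.1 includes a white-cell differential among the safety laboratory tests. Sections 10.6 and 10.7 list hematology beside chemistry at Months 2, 4, 6 and 12, at the annual visits and at the Common Study End Date visit.

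**The concern.** The repeat evaluation is where a participant with an enzyme alert is sorted into restart or permanent stop. One of the facts that decides this, the eosinophil percentage, is not among the required tests. In a participant with no listed symptom, only that percentage separates the two tiers.

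At stake is re-exposure. Someone who met a permanent-stop criterion could be given drug again, at the investigator's discretion, once the enzymes settle. The protocol treats the liver as a matter for care: Section 4.7.1 names it as the apparent primary target organ of toxicity in nonclinical studies, and Section 12.2.7 makes liver disease an adverse event of special interest.

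**Working it through.** No sample size, power or error-rate figure is involved, so the check sets the stopping rules beside the tests that feed them.

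| Input to the Section 7.3.1 liver rules | Scheduled safety tests (12.1.2.1) | Required repeat (12.1.2.2.1) |
|---|---|---|
| ALT, AST | yes | yes |
| Bilirubin | yes | yes |
| INR | no | yes |
| Eosinophils | yes, in the differential | no |
| Symptoms and signs | not a laboratory item | asked about |

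The INR row matters. INR is absent from the scheduled panel and present on the repeat list, and Section 7.3.1 uses the repeat INR to decide on a permanent stop. The repeat list is therefore meant to supply inputs to the rules, and eosinophils are the one laboratory input it does not supply.

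Next, follow a participant with ALT or AST above 3 X ULN and no listed symptom.

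1. **The alert comes from a scheduled draw and the paired count shows more than 5% eosinophils.** The permanent tier applies at once. There is no gap.
2. **The alert comes from a scheduled draw, the paired count is normal, and eosinophilia develops while the enzymes are still above 3 X ULN.** The 72-hour repeat does not measure eosinophils. The weekly follow-up covers abnormal values, and the eosinophil count was not abnormal when last seen. Scheduled hematology is discretionary while the participant is off drug. If the enzymes recover, drug can be resumed with the criterion met but unseen.
3. **The alert comes from a draw without a paired count,** such as a local or off-schedule test. No count is required then, at the repeat or during follow-up. The result is the same as in case 2.

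Case 1 should be the usual one: Sections 10.6, 10.7 and 12.1.2.1 pair hematology with all nine scheduled post-randomization chemistry draws (Months 2, 4, 6, 12, 24, 36, 48 and 60, and the end-of-study visit). The gap is cases 2 and 3.

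**The case against.** The best answer is that the criterion is already handled where it is first applied. The permanent tier acts immediately, so it is judged on the alert draw, and every scheduled chemistry draw has a differential with it. The protocol requires no off-schedule liver draws other than the repeats and follow-up. The lists set a minimum, local testing is allowed, and a site may add a count. Drug is off in both tiers. All of this stands, and it limits the point to cases 2 and 3. It does not close them: permission to add a count is not a requirement, and restarting depends on a criterion that the required repeat tests do not measure.

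A second answer is that Section 7.3 blurs the distinction: "All study drug discontinuations should be considered temporary interruptions because participants are allowed to restart medication at any time". This softens the permanent tier, but the passage goes on to require that the condition behind the interruption has resolved. For eosinophilia that also needs a count. Section 7.3 also keeps "The participant meets any of the criteria specified in Section 7.3.1" as a reason to be recorded. That entry covers both tiers, so the record alone would not show the difference.

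Two stronger readings are tempting, and the documents support neither. A reader might infer that the eosinophil criterion can never be assessed; the scheduled differentials show otherwise. A reader might also take the apparent blanks for hematology in Appendix A at Randomization, Month 6 and Month 12 as missing tests. Sections 10.4, 10.6 and 12.1.2.1 call for hematology at those visits, and the table as available is damaged, so nothing should be built on the blanks.

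**Conclusion.** The omission is real and small. Eosinophilia that first appears after the alert draw, or that accompanies an alert from a draw without a count, would not be found by any mandated test before drug is resumed in a participant with no listed symptom.

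This rests on three readings: eosinophilia alone satisfies the criterion, it may be met on a later draw while enzymes remain above 3 X ULN, and the required repeat is limited to the two cited lists. The documents give no frequency for isolated eosinophilia with an enzyme alert, so no number of participants can be stated. Sample size, error control and the primary analysis are not touched. It is best labelled a cheap improvement to patient safety, of minor weight.

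**What to change.** Add a complete blood count with differential to the repeat list in Section 12.1.2.2.1. State that it also applies at follow-up draws while ALT or AST remains above 3 X ULN; otherwise a normal count at 72 hours would end the monitoring of eosinophils. Thresholds and actions stay as they are.

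The cost is one extra tube at draws already required. A required count will sometimes find eosinophilia from an unrelated cause and so bring a permanent stop, but it does so under a threshold the protocol already contains.

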7.4. Follow-up after Early Study Drug Discontinuation or Withdrawal

The participant has the right to withdraw from the study at any time. Nevertheless, in this study, investigators will be trained to minimize full withdrawals from study wherever possible. Every attempt will be made to prevent missing data and to obtain complete follow up of all participants at the end of the study. Participants who interrupt or discontinue study drug will be encouraged to remain in the study and asked to attend the remaining study visits as outlined in the protocol until the end of the study if possible, or at a minimum to maintain contact with the investigator and site to allow for the assessment of the occurrence of primary endpoint events.

Participants who choose to withdraw consent will be asked to document their withdrawal of consent in writing and acknowledge that they have been offered options for limited participation. For participants who withdraw consent, assessment of the participant's health status at the end of the study will be performed in compliance with local privacy laws, regulations, and practices and may include a phone call to the participant or next-of-kin to ascertain vital status and occurrence of primary endpoint events. Unless revoked, further contact in the case of withdrawal from the study will occur consistent with methods listed in the informed consent form.

Although a participant is not obligated to give his/her reason for withdrawing prematurely, the investigator will make a reasonable effort to obtain the reason while fully respecting the participant's rights. The reason for withdrawal from the study must be documented in the eCRF. The CSR will include the reason(s) withdrawal from the study.

Withdrawn participants will not be replaced.

7.4.1. Lost-to-Follow-up

As adherence to the protocol, ascertainment of primary study endpoints, vital status, and minimization of participants who are lost-to-follow-up are paramount, participant contact information will be collected centrally as specified in the written informed consent for participation in the study. Text messaging, newsletters, and a web-based study participant portal

Confidential K-877-302 Study Protocol

Version 3 dated 18-Mar-2020

may be employed for purposes of retention, compliance, and to minimize participants being lost-to-follow-up. Local IRB/IEC/REC regulations will apply.

For participants who are lost-to-follow-up (ie, those participants whose life or death status is unclear because they fail to appear for study visits without stated intention to withdraw or fail to contact the site), the investigator must show due diligence in the steps taken to contact participants. Steps taken may include telephone calls to the participant or next-of-kin, e-mail, or registered letters. For participants who are lost-to-follow-up, the site will be required to complete the Missed Visit eCRF at regularly scheduled study visits and to document, in a separate eCRF designed for this purpose, the attempts made to contact the participant. If contact is reinitiated, it is possible for the participant to return for clinic visits with resumption of study activities based upon their original randomization date.

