To assess the effect of non-informative censoring on the primary outcome, analyses will be performed following the reference-based method outlined by Carpenter, Roger, and Kenward⁶⁹ and detailed in the Statistical Analysis Plan using the piece-wise exponential method described by Lipkovich at al.⁷⁰ For those participants who were lost-to-follow-up, event status after the time of last observation is imputed using the distribution of retrieved dropouts for each arm. Retrieved dropouts are defined as participants who are no longer taking study drug but have agreed to continue to be followed. Other imputation models for missing data will also be explored for their effect on the primary outcome, including models that use the entire placebo group as the reference.

Separate proportional hazards models will also be used to compare the effects of pemafibrate treatment on time to each of the individual components of the composite primary endpoint. Analyses will use methods of competing risks survival analysis and compare the relative effects of randomized treatments on the different components of the composite outcome.^{72, 73} The approach of Lunn and McNeil⁷² provides a readily accessible implementation of a classical approach to competing risk analysis developed by Kalbfleisch and Prentice.⁷⁴

Secondary lipid efficacy endpoints will be analyzed using analysis of covariance (ANCOVA) with a retrieved dropout-based pattern mixture model. Participants with missing data will be imputed using the distribution of retrieved dropouts for each arm, where retrieved dropouts are defined as participants who are no longer taking study drug but have agreed to continue to be followed. Imputed data will be analyzed using an ANCOVA model with baseline measurement as a covariate and the treatment arm and randomization strata as fixed effects.

While all primary analyses are on the ITT population, a Per-Protocol population will also be analyzed which will be limited to participants with no major protocol deviations. Sensitivity analyses for the primary efficacy endpoint will also be conducted examining the effect of compliance and escalation of other lipid-lowering medications. Longitudinal analyses will quantify the impact of pemafibrate on lipid levels, biomarkers of inflammation, and glycemic parameters and other prespecified exploratory lipid and non-lipid biomarkers (Tertiary Endpoints: Section 5.3.1).

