17.3. Written Informed Consent

Before any study-specific procedures or assessments are conducted, participants who have had the protocol fully explained by the responsible investigator and who are willing to participate in the study must read, sign, and date an ICF. The Principal Investigator(s) at each center will ensure that the participant is given full and adequate oral and written information about the nature, purpose, and possible risks and benefits of the study. Participants must also be notified that they are free to discontinue from the study at any time. The participant should be given the opportunity to ask questions and allowed time to consider the information provided.

The Principal Investigator(s) must maintain the original, signed ICF. A copy of the signed ICF must be given to the participant.

As described in the informed consent documents, participation in the genetic biobanking portions of the study will be on an "opt-out" basis and are not a requirement for participation in the main study.

The ICF will be used to explain the risks and benefits of study participation to the participant in simple terms before the participant will be entered into the study. The ICF contains a statement that the consent is freely given, that the participant is aware of the risks and benefits of entering the study, and that the participant is free to withdraw from the study at any time. The ICF will describe all levels of participation, including passive follow-up and contact of participants who stop attending study visits to confirm vital status and endpoint occurrence at study end. Written consent must be given by the participant and/or legal representative, after the receipt of detailed information on the study.

The investigator is responsible for ensuring that informed consent is obtained from each participant or legal representative and for obtaining the appropriate signatures and dates on the informed consent document prior to the performance of any protocol procedures and prior to the administration of study medication. The investigator will provide each participant with a copy of the signed and dated consent form.

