8.4. Analysis of the Primary Efficacy Endpoint

8.4.1. Primary Efficacy Analysis

The primary endpoint of the trial is the time from randomization to the first occurrence of any component of the clinical composite endpoint of nonfatal myocardial infarction, nonfatal ischemic stroke, cardiovascular death, and coronary revascularization.

Patients who do not have an event will be censored at withdrawal of consent, end of study, or death. The censor date will be the date of withdrawal of consent for follow-up, CSED or the subject's last assessment, or death, whichever comes first. The time to event/censoring in days will be derived as (Date of First Occurrence of Event/Censoring – Date of First Dose) +1. The primary analysis of the trial will use a likelihood ratio test based on a proportional hazards model stratified on sex, prior history of CVD, and statin use at baseline to test the null hypothesis of no association between assignment to active K-877 and the rate of the primary endpoint. All analyses will classify patients according to their randomized treatment assignment, i.e. according to the intention to treat principle, and will base evaluation of statistical significance on a two-sided test with level 0.05. The estimated relative hazard in the K-877 group compared to the placebo group with an accompanying 95% confidence interval will quantify the treatment effect. If this relative hazard is less than 1, then 100*(1-estimated relative hazard) will be defined as the percent reduction in hazard associated with K-877 treatment. Rates of occurrence of the primary endpoint will be defined as the total number of subjects who have this event in a treatment group per 100 person-years of follow-up. Estimates of the probability of the primary

```
Kowa Research Institute, Inc.
Statistical Analysis Plan – Protocol K-877-302 (PROMINENT)
```

endpoint by time after randomization within treatment groups will be based on the method of Kaplan and Meier.

Analysis will be implemented using the SAS® procedure PHREG as follows:

```
PROC PHREG DATA = ...;

CLASS TREATMENT (ref='2');

MODEL AVAL*CNSR(1) = TREATMENT;

STRATA SEX CVD STATIN;

HAZARDRATIO TREATMENT / ALPHA=0.05;

RUN;

where AVAL = time to event

TREATMENT = Randomized treatment group (pemafibrate and placebo)

CNSR = Censoring variable - 0 = Event, 1 = Censored

SEX = sex

CVD = prior history of CVD

STATIN = statin use at baseline
```

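### The protocol's imputation check on censoring covers only participants of unknown vital status, so it omits those censored at withdrawal of consent and those known alive with unknown endpoint status

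*Protocol*

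**What the plan says.** **Purpose of the check (Protocol 14.5).** "To assess the effect of non-informative censoring on the primary outcome, analyses will be performed following the reference-based method". The method uses retrieved dropouts (off study drug but still followed) in each arm as the source for imputation.

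**Who is imputed (Protocol 14.5).** "For those participants who were lost-to-follow-up, event status after the time of last observation is imputed". The same section adds: "Other imputation models for missing data will also be explored for their effect on the primary outcome". No participant set is given for these further models, although one example uses the whole placebo group as reference. For the lipid endpoints, 14.5 imputes all participants with missing data.

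**Who counts as lost (Protocol 7.4.1).** The section limits the term, by an explicit *ie*, to "those participants whose life or death status is unclear because they fail to appear for study visits without stated intention to withdraw", or who do not contact the site. It also provides for return: "If contact is reinitiated, it is possible for the participant to return for clinic visits".

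**Withdrawal of consent (Protocol 7.4).** This is a separate category. Status at study end is sought where local law allows and "may include a phone call to the participant or next-of-kin to ascertain vital status and occurrence of primary endpoint events".

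**Primary censoring.** Protocol 14.4 stops follow-up time at the event, death, end of trial or withdrawal of consent. SAP 8.4.1 states: "The censor date will be the date of withdrawal of consent for follow-up, CSED or the subject's last assessment", or death, whichever is first.

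**SAP sensitivity analyses.** SAP 6.7.1 assumes non-informative censoring for the main analyses. SAP 8.4.2 lists two main types of sensitivity analysis, Per-Protocol and changes in lipid-lowering therapy, plus summaries by year. It lists no imputation for censored participants. SAP 7.1 has a broader notion of incomplete follow-up (anyone neither known dead nor assessed at study end) but ties it to no analysis.

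**The concern.** A check on censoring should reach everyone whose primary endpoint follow-up stops early for a reason other than death. Withdrawal of consent is the one such reason that Protocol 14.4 names, and it may follow side effects or declining health. The named check leaves it out.

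The definition in 7.4.1 turns on vital status, whereas three of the four primary components are nonfatal. Learning only that a participant is alive removes that person from the lost group without telling us whether an infarction, ischemic stroke or revascularization occurred.

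Both groups then stay non-informatively censored in the analysis meant to question that assumption. Protocol 14.7 and SAP 5.2 also ask the DSMB to consider the sensitivity analysis for loss to follow-up before early stopping, so its coverage bears on that decision as well as on the final report.

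**Working it through.** **1. Coverage, from the text.** Participants without an event whose endpoint follow-up ends before the Common Study End Date (CSED), other than by death:

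| Group | Primary analysis | Named check in 14.5, read with 7.4.1 |
|---|---|---|
| Consent withdrawn, endpoints not obtained later | censored at withdrawal | not imputed |
| Stopped attending, vital status unclear | censored at last assessment | imputed |
| Stopped attending, known alive, endpoints unknown | censored at last assessment | not imputed |
| Stopped attending, endpoints later obtained | followed | little or nothing to impute |

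**2. The plan's own figures reproduce.** Inputs from Protocol 14.2: HR 0.834, two-sided alpha 0.05, power 90%, 1:1 allocation.
- Schoenfeld: 4(1.960 + 1.282)² / (ln 0.834)² = 1,276 events. Freedman: 1,283. The protocol states 1,279.
- 1,279 × 1.019 = 1,303.3, hence 1,304.
- With 3-year uniform accrual and 1% annual loss, 1,304 events are reached at 5.97, 5.41 and 4.97 years for placebo rates of 3.5, 4.0 and 4.5 per 100 person-years. Table 6 gives 5.9, 5.3 and 4.9.

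**3. Early censoring at the planned 1% per year.** For n participants with event hazard λ, loss hazard η = 0.01, accrual R = 3 years and duration T, the expected number censored early is

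n · η/(λ+η) · {1 − [e^(−(T−R)(λ+η)) − e^(−T(λ+η))] / [R(λ+η)]}

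- Placebo arm, λ = 0.045, T = 4.97: 5,000 × 0.1818 × {1 − (0.8973 − 0.7608)/0.165} = 157. The pemafibrate arm gives 159, total 316.
- At a placebo rate of 3.5: 202 + 205 = 407.
- Primary events expected in their unobserved time, at each arm's own hazard: about 23 to 30, which is 1.8% to 2.3% of 1,304.

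The documents do not split this total by vital status or withdrawal.

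**4. Effect on the hazard ratio, placebo hazard after censoring.** Assumptions: loss 1% per year (protocol); withdrawal a further 1% per year (assumed); placebo rate 4.5, HR 0.834, R = 3, T = 5.
- Observed on pemafibrate: 591.6 events in 15,762 person-years, rate 0.03753.
- Each censoring cause adds about 12.8 imputed events in 285 person-years to that arm. The placebo rate stays at 0.045.
- Lost only: (591.6 + 12.8)/(15,762 + 285) = 0.03766. HR 0.8369, ratio to 0.834 = 1.0035.
- All early-censored: (591.6 + 25.6)/(15,762 + 570) = 0.03779. HR 0.8398, ratio 1.007.

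Simulation gives the same: about 0.7% for all and 0.35 to 0.4% for the lost only.

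**5. What such a shift does.** With z = |ln HR| · √1304 / 2, the significance limit is HR 0.897.
- HR 0.834: p = 0.001. Multiplied by 1.007: p = 0.002.
- HR 0.89: p = 0.035. Multiplied by 1.0035: p = 0.041. Multiplied by 1.007: p = 0.048.

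**The case against.** **The link between sections is not explicit.** Section 14.5 does not cite 7.4.1, whose definition sits in a section on retention and tracing. The documents also use the term loosely: the same 1% is loss to follow-up in Protocol 14.2 and attrition due to drop-outs in the synopsis. This stands as a reason to call the wording ambiguous. But 7.4.1 is the only definition given, and the lipid analysis in the same section uses broader wording.

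**Other imputation models are promised.** They could reach the omitted groups. Their set is undefined and they are only to be explored, so they do not close the gap.

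**Tracing seeks more than vital status.** A reader might infer that everyone later traced as alive is left out. The documents do not support that. Protocol 17.3 foresees "passive follow-up and contact of participants who stop attending study visits to confirm vital status and endpoint occurrence at study end", 7.4 seeks endpoint events even after consent is withdrawn, and SAP 5.3 continues follow-up of withdrawers and of those who miss the final visit. Where endpoints are obtained, nothing material is left to impute.

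**The check need not be nearly empty.** A reader might also infer that it would test almost no one. If 5% to 10% of those censored early had unknown vital status, about 16 to 41 participants and 1 to 3 imputed events would remain, but no document gives such a share. If the planned 1% were all loss in the sense of 7.4.1, the check would cover 316 to 407 people.

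**Large shifts need unsourced inputs.** With 1% withdrawal added to 1% loss and a post-censoring hazard on pemafibrate of 1.5 to 2 times placebo, the HR rises by 2.7% to 4.6% for all early-censored, against 1.4% to 2.3% for the lost only. Neither the multiplier nor the added withdrawal comes from the documents. These are stress scenarios.

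**Conclusion.** The point holds as one of scope: a stated rule is too narrow for its stated purpose. Read with 7.4.1, the only imputation check with a named participant set omits withdrawals of consent and participants known alive with unknown endpoint status. The SAP does not repair this, because it describes no censoring imputation for the primary endpoint; the relevant method papers appear only in its reference list. Restoring the 14.5 wording there unchanged would bring the narrow set with it.

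The likely size is small. Under the step 4 assumptions, the difference between covering all early-censored participants and covering the lost only is about 0.3% on the hazard ratio. Even full coverage leaves the design effect clearly significant, and in the example HR 0.89 stays just below 0.05. The gap matters for a borderline result, or if risk after censoring is markedly worse on pemafibrate. The documents do not support a claim that the trial's conclusion would change. The size of the omitted group remains unknown: 316 to 407 is the total censored early if 1% per year covers every cause, not a count of those omitted.

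**What to change.** In Protocol 14.5 and SAP 8.4.2, before unblinding:

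- Define the imputation set as every participant without a primary event whose last complete ascertainment of all four primary components falls before the CSED for a reason other than death. Include withdrawals of consent and participants with vital status only. Exclude those whose endpoint status is later obtained.
- Impute from the date of that last complete ascertainment.
- Report the number in the set by arm and by reason.
- Use the same set for the loss-to-follow-up check that the DSMB considers under Protocol 14.7 and SAP 5.2.
- Keep the 7.4.1 definition for retention reporting only.

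The cost is revised wording, the addition of the method to the SAP, and a slightly larger imputation run. The sensitivity estimate may be slightly wider or less favourable. The primary analysis does not change.
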